## 4.1 OVERVIEW OF STUDY DESIGN/INTERVENTION

### 4.2 Design

This is a single-institution, single-arm, open-label, phase II study of enzalutamide 160mg by mouth once daily in patients with AR+ recurrent or advanced ovarian, primary peritoneal or fallopian tube cancer. After signing a screening consent, patients archival tissue will be evaluated for degree of AR positivity by AR staining. Patients with no archival tissue available will undergo a biopsy (using the modality deemed most appropriate by the patient's physician) for collection of tumor tissue for AR positivity by IHC. Only AR+ patients, defined as  $\geq 5\%$  positivity by IHC, will be included. All IHC testing will be performed in the MSKCC Clinical CLIA approved laboratory.

All eligible patients will have measurable disease by RECIST 1.1 criteria and will have received one, two or three prior cytotoxic treatments for their disease. A maximum of 19 enrolled patients will have 3 prior therapies. Patients will be treated until POD, intolerable toxicity or withdrawal of consent.

The primary endpoint of this trial is to determine the proportion of women with AR(+) ovarian, primary peritoneal, or fallopian tube cancer who survive progression free for at least 6 months and the proportion of patients who have objective tumor response (complete or partial response) by RECIST 1.1 criteria when treated with enzalutamide 160mg PO QD.

The frequency and severity of adverse events as assessed by NCI CTCAE version 4.0 will be described. Optional tumor biopsies will be performed at end of treatment, in order to explore the effect of enzalutamide on tumor AR expression.

### 4.3 Intervention

Prior to initiation of treatment patients will sign a screening informed consent form for AR IHC testing. If archival tissue is not available then the patient must consent to a biopsy. In cases where multiple blocks are available staining will be performed on unstained slides from 3 separate blocks. If  $\geq 5\%$  AR tumor staining is seen on  $\geq 1$  slide the tumor will be considered to be AR+. Only those patients found to have  $\geq 5\%$  AR by IHC will be eligible for treatment.

All enrolled patients will be treated with enzalutamide 160mg PO QD. Study drugs will be self-administered by patients. A cycle is 28 days. Patients will be required to maintain a pill diary to record each dose of drug taken (see **Appendix A**). All toxicities will be graded using CTCAE version 4.0. Toxicities will be evaluated during physician assessments performed every 2 weeks during the first cycle and every 4 weeks during subsequent cycles of treatment with enzalutamide.

Patients will continue to receive study treatment until POD (as defined by RECIST 1.1), unacceptable toxicity or withdrawal of consent.

Dose modifications will be allowed as described in **Section 9**.

Enrollment will proceed following a safety lead-in of 15 patients. If  $\geq 5$  patients develop any of the following events classified as dose-limiting toxicity (DLT) during the **first 28 days** of treatment the study will be halted and the PI will examine the toxicity profile and determine whether lower doses will be added. DLT is defined as:

- Any event consistent with a seizure of any grade
- Grade  $\geq 3$  diarrhea, nausea, or vomiting that does not improve to Grade 1 within 14 days of initiating standard of care therapy
- Grade  $\geq 3$  decreased platelet count with associated bleeding
- Grade  $\geq 3$  absolute neutrophil count (ANC) that persists for 7 or more days or that is associated with fevers (febrile neutropenia)
- Any other  $\geq$  Grade 3 non-hematologic toxicity determined to be related to study drug

If  $< 5$  patients develop one of the above events during the first 28 days of treatment then enrollment will proceed following a two-stage design. A total of 28 patients (including the first 15) will be enrolled during the first stage. If 3 or more patients have clinical response or 5 or more patients have no progression/death at 6 months, then the study will open to the second stage of accrual. No more than 9 out of the 28 patients (1/3) enrolled during stage I will have 3 prior therapies. In stage II, an additional 30 patients will be enrolled. At the end of stage II, if at least 7 of 59 (28+30=58) patients have clinical response or at least 13 of 59 patients survive progression free for 6 months, this will be considered as a positive trial.

Patients will be evaluated for radiographic response every 2 cycles (8 weeks) and at the end of study. Response is defined as the best over-all response achieved by RECIST 1.1 criteria while on study treatment.

At end of treatment an optional tumor biopsy will be performed in patients who consent to this procedure.

## **5.0 THERAPEUTIC/DIAGNOSTIC AGENTS**

### **5.1 Enzalutamide**

Enzalutamide is a white to off white solid. It is insoluble in water. It is supplied as soft gelatin filled capsules that are filled to contain 40 mg of active pharmaceutical ingredient.

Each patient will self-administer 160mg (4 capsules) PO daily and should be instructed to take the 4 enzalutamide capsules with a glass of water at approximately the same time each day. Each dose should be recorded in the patient's pill diary. Enzalutamide can be taken with or without food. Patients should not make up missed or vomited doses; patients

should resume dosing at their scheduled time the next day unless otherwise instructed. Patients should not take enzalutamide if more than 12 hours have lapsed since the missed dose.

## **5.2 Storage and Labeling**

Enzalutamide should be stored in a secure location with limited access at 77°F (25°C), with excursions permitted to 59°F to 86°F (15°C to 30°C). Bottles will be labeled with the study protocol number, lot number, contents, directions for use, storage directions, clinical trial statement, and Sponsor (Medivation, Inc.). Patients will be instructed to store study drug at room temperature and out of reach of children.

## **6.1 CRITERIA FOR SUBJECT ELIGIBILITY**

### **6.2 Subject Inclusion Criteria**

- Advanced or recurrent epithelial ovarian, fallopian tube or primary peritoneal carcinoma. Histologic documentation of the original primary tumor is required via the pathology report
- AR expression  $\geq 5\%$  by IHC. In cases where multiple blocks are available staining will be performed on unstained slides from 3 separate blocks. If  $\geq 5\%$  AR tumor staining is seen on  $\geq 1$  slide the tumor will be considered to be AR+.
- Patients with the following histologic cell types are eligible: serous adenocarcinoma, endometrioid adenocarcinoma, mucinous adenocarcinoma, undifferentiated carcinoma, clear cell adenocarcinoma, mixed epithelial adenocarcinoma, transitional cell carcinoma, malignant Brenner's tumor, or adenocarcinoma not otherwise specified
- Measurable disease as defined by RECIST 1.1. Measurable disease is defined as at least one lesion that can be accurately measured in at least one dimension. Each lesion must be  $\geq 10\text{mm}$  when measured by CT, MRI or caliper measurement by clinical exam; or  $\geq 20\text{mm}$  when measured by chest x-ray. Lymph nodes must be  $\geq 15\text{mm}$  in short axis when measured by CT or MRI
- Patients must have had one prior platinum-based chemotherapeutic regimen for management of primary disease
- Patients may have received, but are not required to have received, one or two additional cytotoxic regimens for management of recurrent or persistent disease
- Patients who have received only one prior cytotoxic regimen (platinum-based regimen for management of primary disease), must have a platinum-free interval of less than 12 months, or have progressed during platinum-based therapy, or have persistent disease after a platinum-based therapy
- Patients are allowed to receive, but are not required to receive, non-cytotoxic therapy (such as bevacizumab) as part of their primary treatment regimen. Patients are allowed to receive, but are not required to receive, non-cytotoxic therapy for management of recurrent or persistent disease

- Must be  $\geq 18$  years of age
- Karnofsky Performance Status (KPS) of  $\geq 70\%$
- Life expectancy of  $\geq 12$  weeks
- Women of child-bearing potential must have a negative pregnancy test within 14 days prior to commencement of study treatment
- Women of child bearing potential must use an effective form of contraception during study and for at least 6 months after completion of study treatment
- Recovery from effects of recent surgery, radiotherapy, or chemotherapy
  - At least 4 weeks out from their last dose of radiation therapy
  - At least 4 weeks post-op from any major surgical procedure
  - At least 3 weeks out from their last dose of chemotherapy and/or biologic/targeted therapy
- No prior hormonal therapy for treatment of cancer within the past 21 days
- Absence of any psychological, familial, sociological or geographic condition that would potentially hamper compliance with the study protocol
- Prior use of or participation in a clinical trial evaluating and agent that either blocks androgen synthesis (e.g. abiraterone acetate, TAK-700, TAK-683, TAK-448) or targets the AR (e.g., bicalutamide, BMS-641988) (patients who are known to have only received placebo in these studies are eligible)
- Laboratory Test Findings performed within 14 days prior to initiation of study drug showing:
  - Bone marrow function:
    - Absolute neutrophil count (ANC)  $\geq 1,000/\text{mcL}$
    - Platelets  $\geq 100,000/\text{mcL}$
    - Hemoglobin  $\geq 8 \text{ g/dL}$
  - Renal function:
    - Creatinine  $\leq 1.5 \times \text{ULN}$
  - Hepatic function:
    - Bilirubin  $\leq 1.5 \times \text{ULN}$
    - AST and ALT  $\leq 2.5 \times \text{ULN}$
- Resolution of all acute toxic effects of prior therapy to NCI CTCAE (Version 4.0) Grade  $\leq 1$ , with the exception of unresolved Grade 2 neuropathy and Grade 2 alopecia, which are allowed
- Patients must be able to swallow tablets whole, without crushing

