Earlier studies examining alternative methods of androgen inhibition in ovarian, primary peritoneal, and fallopian tube cancer have all been performed in an unselected population of women, typically with multiple prior lines of therapy. Drawing on recent advances, the present study will be performed in a selected population of women with AR+ advanced ovarian, primary peritoneal, or fallopian tube cancer ( $\geq 5\%$  by IHC) with measurable disease. Enrolled patients will have had only one, two or three prior cytotoxic therapies. All enrolled patients will be treated with enzalutamide 160 mg PO QD until progression of disease (POD), unacceptable toxicity or withdrawal from study. Based on the prior response rates that have been seen with targeted therapy of recurrent or advanced ovarian cancer (Table 1), and the relatively benign side effect profile of enzalutamide, we will consider this treatment worthy of further study if there is an observed response rate of 12.5% or an observed 6 month PFS interval is seen in 22.5% of patients. Given that enzalutamide 160 mg PO has not previously been administered to women with ovarian cancer this study will utilize a safety lead-in. If  $\geq 5$  out of the first 15 patients develop a DLT during the first 28 days of treatment then the study will be put on hold. If this does not occur then enrollment will continue.

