### 6.3 Subject Exclusion Criteria

- A history of another invasive malignancy (other than non-melanoma skin cancer or curatively treated in situ carcinoma) with evidence of disease within the past 3 years
- Use of a medication known to lower the seizure threshold within 28 days of first dose of study drug (see **Appendix B** for a representative list of medications known to lower the seizure threshold)
- Known brain metastasis

- History of seizure
- Uncontrolled hypertension (systolic BP  $\geq$  160 mmHg or diastolic BP  $\geq$  95mmHg) despite medical treatment. Patients with a history of hypertension are allowed provided blood pressure is controlled by anti-hypertensive treatment.
- Clinically significant heart disease as evidenced by myocardial infarction or arterial thrombotic event within the past 6 months, severe or unstable angina, or New York Heart Association (NYHA) Class II-IV heart disease or cardiac ejection fraction measurement of  $<$  50% at baseline
- Refractory nausea and vomiting, requirement for parenteral hydration and/or nutrition, drainage gastrostomy tube, malabsorption, external biliary shunt, or significant small bowel resection that would preclude adequate study drug absorption
- Anticipated or ongoing administration of anti-cancer therapies other than those administered in this study

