### 9.3 Drug Interactions

Any medication (see **Appendix B** for representative medications) that may predispose the patient to seizure disorder should be stopped at least 4 weeks prior to starting treatment with enzalutamide.

The following medications or therapies are prohibited during the receipt of study drug:

- Medications, including herbal therapies, with an antitumor effect
- Any investigational agent
- AR antagonists
- 5- $\alpha$  reductase inhibitors
- Androgens
- And medication (see Appendix B for representative medications) that may predispose the patient to seizure

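### An inclusion bullet on prior androgen-synthesis or AR-targeted therapy has no negation, so as written it requires the exposure that its own placebo exception implies is barred; Section 6.3 does not cover the point.

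*Combined protocol and SAP*

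**What the plan says.** Section 6.2 (Subject Inclusion Criteria) contains a bullet beginning "Prior use of or participation in a clinical trial evaluating and agent that either blocks androgen synthesis". It continues to agents that target the AR, names examples of both classes, and closes with a parenthesis: "patients who are known to have only received placebo in these studies are eligible". No word of negation precedes it. It stands mid-list, between the bullet on conditions that could hamper compliance and the bullet on laboratory values.

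Other statements that bear on prior or concurrent therapy of this kind:

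- Section 6.2, hormonal therapy: "No prior hormonal therapy for treatment of cancer within the past 21 days".
- Section 6.2, recovery from earlier treatment: "At least 3 weeks out from their last dose of chemotherapy and/or biologic/targeted therapy".
- Section 6.2, non-cytotoxic therapy: "Patients are allowed to receive, but are not required to receive, non-cytotoxic therapy for management of recurrent or persistent disease".
- Section 6.3 (Subject Exclusion Criteria), the nearest of eight bullets: "Anticipated or ongoing administration of anti-cancer therapies other than those administered in this study".
- Section 9.3 (Drug Interactions) lists AR antagonists under "The following medications or therapies are prohibited during the receipt of study drug".
- Section 3.5 describes the population by AR positivity, measurable disease and cytotoxic history: "Enrolled patients will have had only one, two or three prior cytotoxic therapies". Sections 1.0 and 4.2 do the same. None of them mentions earlier AR-directed treatment.

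**The concern.** An inclusion criterion is something a patient must satisfy. Under that heading, an un-negated bullet on prior exposure admits only patients who have already had an androgen-synthesis blocker or an AR-targeted agent, or who took part in a trial of one. That cannot be squared with the rest of the plan, and the bullet's own parenthesis points the other way.

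This is an operative rule. Section 15.2 has staff confirm eligibility as the criteria section defines it and complete a protocol-specific checklist, and Section 16.2 provides for compliance audits. In a single-arm trial, the response rate and the 6-month progression-free survival (PFS) rate depend directly on who is enrolled, and this criterion concerns earlier treatment of the pathway under test. At stake are whether patients are registered consistently, whether an audit can classify them correctly, and whether the reported population can be described without dispute.

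**Working it through.** **Text check.** No formula decides the main point. Three kinds of patient, otherwise eligible, can be taken through the three ways of reading the bullet.

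| Patient | Followed literally (exposure required) | Read as a bar | Set aside as an error |
|---|---|---|---|
| No prior AR-directed therapy | Fails | Passes | Passes |
| Prior active agent, washout complete | Passes | Fails | Passes |
| Placebo only in such a trial | Passes | Passes (exception) | Passes |

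1. *Literal reading.* Trial participation alone already satisfies the bullet, so a placebo-only patient would qualify without the parenthesis, which then does no work. This reading also conflicts with the Section 6.2 bullet that makes non-cytotoxic therapy for recurrent or persistent disease optional.
2. *Read as a bar.* The parenthesis does what an exception should do: it readmits patients who were never exposed. This is the natural sense, but it has to be inferred. The bullets just before it that bar something say so, opening with "No prior hormonal therapy for treatment of cancer within the past 21 days" in one case and with a requirement of absence in the other.
3. *Set aside.* Nothing else stops an exposed patient. None of the eight bullets in Section 6.3 covers past exposure; the nearest is limited to anticipated or ongoing therapy. Section 6.2 leaves washouts of 21 days (hormonal) and 3 weeks (chemotherapy, biologic or targeted), and Section 9.3 applies only while study drug is being taken.

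The bullet is complete, with no gap or redaction, so text extraction does not explain it.

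**Illustration of size.** The documents give no prevalence of prior exposure and no figure for benefit in exposed patients. Two assumptions are therefore needed: a fraction f of enrolled patients is exposed, and those patients have the null rates.

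Inputs from Sections 4.3 and 14.2:
- Null rates are 5% (response) and 15% (6-month PFS); target rates are 20% and 30%.
- Stage I has 28 patients and continues with at least 3 responses or at least 5 patients progression-free at 6 months.
- The trial is positive with at least 7 responses or at least 13 patients progression-free at 6 months.
- Stage II has 30 patients in Section 4.3 and in the accrual paragraph of Section 14, giving N = 58. It has 31 in the sample-size text, giving N = 59. Both were run.

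Diluted rates: response = 0.20 − 0.15f; PFS = 0.30 − 0.15f. An endpoint that does not improve stays at its null rate. Power is by exact enumeration of both stages. The correlated case uses the plan's joint probability, 0.90 × the smaller rate.

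Reproducing the plan at f = 0, N = 58:

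| Case | Independent (plan) | Correlated (plan) |
|---|---|---|
| Both null | 0.099 (0.10) | 0.090 (0.09) |
| PFS improves only | 0.905 (0.90) | 0.900 (0.90) |
| Response improves only | 0.939 (0.94) | 0.918 (0.92) |
| Both improve | 0.994 (0.99) | 0.967 (0.97) |

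Power at N = 58 as f rises:

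| Case | f = 0 | 2% | 5% | 10% | 20% |
|---|---|---|---|---|---|
| PFS only, independent | 0.905 | 0.897 | 0.884 | 0.860 | 0.801 |
| PFS only, correlated | 0.900 | 0.892 | 0.879 | 0.854 | 0.794 |
| Response only, independent | 0.939 | 0.933 | 0.923 | 0.905 | 0.855 |
| Both, independent | 0.994 | 0.993 | 0.992 | 0.987 | 0.972 |
| Both, correlated | 0.967 | 0.963 | 0.957 | 0.944 | 0.909 |

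Over all three improvement scenarios, both correlation models and N = 58 or 59, the loss is 0.1–0.8 points at 2%, 0.3–2.1 at 5%, 0.6–4.6 at 10% and 2.0–10.7 at 20%. Type I error does not move with f in this model, because exposed patients carry the null rates.

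**The case against.** The best reply is that no informed investigator would follow the literal text. The parenthesis reveals the intent, Section 6.2 elsewhere makes non-cytotoxic therapy optional, and the design summaries ask for no AR-directed history. On this view it is a drafting slip, the realistic risk is confined to the occasional exposed patient, and the checklist used at registration may already carry the intended sense.

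Much of this is fair. The intent can be guessed, and the conflict with the placebo exception is by implication: placebo-only patients could formally be an additional eligible group. The checklist is not among the documents, so actual mis-enrolment is possible but not shown. It is also right that a dropped negative explains the text as well as a misplaced exclusion does, since Section 6.2 already holds negatively worded conditions. If the negative was simply lost, the silence of Section 6.3 is not a second defect. Finally, the larger power losses need a prevalence of 20%. At 5% or below, no scenario falls under 0.879.

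None of this makes the operative text say what is presumably meant. Staff and auditors are directed to that text, and it gives different answers depending on the reader.

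**Conclusion.** The concern holds and must be fixed. An inclusion bullet on prior androgen-synthesis or AR-targeted therapy lacks a negation, conflicts with its own placebo exception, and is not repaired elsewhere. Followed literally it fails the ordinary unexposed patient; set aside, it lets exposed patients in after washout. That conclusion rests on the wording alone and is held with high confidence.

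Any effect on the efficacy result is a possibility only. The power figures depend on an assumed prevalence and on assumed zero benefit in exposed patients; partial benefit would shrink the losses. Section 3.1 says androgen inhibition in ovarian cancer has had little attention in recent years, which suggests, weakly, that exposure is uncommon. The case for acting is the contradictory rule, not the power loss.

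**What to change.** The sponsor should reconcile the bullet in Section 6.2 with its placebo exception and with Section 6.3, and state once how prior exposure to these agents affects eligibility. If a bar is intended, as the parenthesis suggests, either moving the bullet to Section 6.3 or adding a negative where it stands would do. The choice of rule and of placement is the sponsor's. The Eligibility Checklist should then be compared with the reconciled text.

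The cost is a one-line amendment and a checklist check. If the reconciled rule bars exposed patients, some accrual could be lost. Section 14 plans 9 + 10 = 19 months of accrual. If that plan counts exposed patients, the extension is 19/(1 − f) − 19: about 0.4, 1.0, 2.1 and 4.8 months at f = 2%, 5%, 10% and 20%. If the plan already leaves them out, there is no extension.

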### 6.3 Subject Exclusion Criteria

- A history of another invasive malignancy (other than non-melanoma skin cancer or curatively treated in situ carcinoma) with evidence of disease within the past 3 years
- Use of a medication known to lower the seizure threshold within 28 days of first dose of study drug (see **Appendix B** for a representative list of medications known to lower the seizure threshold)
- Known brain metastasis

- History of seizure
- Uncontrolled hypertension (systolic BP  $\geq$  160 mmHg or diastolic BP  $\geq$  95mmHg) despite medical treatment. Patients with a history of hypertension are allowed provided blood pressure is controlled by anti-hypertensive treatment.
- Clinically significant heart disease as evidenced by myocardial infarction or arterial thrombotic event within the past 6 months, severe or unstable angina, or New York Heart Association (NYHA) Class II-IV heart disease or cardiac ejection fraction measurement of  $<$  50% at baseline
- Refractory nausea and vomiting, requirement for parenteral hydration and/or nutrition, drainage gastrostomy tube, malabsorption, external biliary shunt, or significant small bowel resection that would preclude adequate study drug absorption
- Anticipated or ongoing administration of anti-cancer therapies other than those administered in this study

